7.3 Adverse Event Reporting

Both serious and non-serious AEs will be clearly noted in source documentation and listed on study-specific Case Report Forms (CRFs). Non-serious adverse events will be reported annually to FDA via an Annual Report (IND: 123591) and to IRB via Continuing Review. SAEs Grade 3 and above, and all subsequent follow-up reports will be reported to the Stanford Cancer Institute Data and Safety Monitoring Committee (DSMC) using the study specific CRF regardless of the event’s relatedness to the investigation. Following review by the DSMC, events meeting the IRB definition of ‘Unanticipated Problem’ will be reported to the IRB using eProtocol within 10 working days of DSMC review, or within 5 working days for deaths or life-threatening experiences.

Adverse events deemed serious, unexpected (i.e. not described in the protocol, Investigator’s Brochure or informed consent documents) and related to study drug must be reported to the IND Holder (CellSight Technologies) using the FDA MedWatch form 3500a within 24 hours of knowledge of event. The IND Holder is responsible for deciding whether the event meets IND Safety Reporting criteria.

If the Principal Investigator determines an unanticipated adverse effect presents an unreasonable risk to subjects, the study will be terminated as soon as possible, but no later than 5 working days after the PI makes the determination and no later than 15 working days after first receiving notification of the effect.

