6 ADVERSE EVENTS AND REPORTING PROCEDURES

7.1 Potential Adverse Events

Risks associated with this Investigational Agent

[¹⁸F]F-AraG has been tested in 6 healthy human volunteers, 3 advanced bladder cancer patients (2 of whom received 2 doses each), 2 breast cancer patients, and 3 squamous cell carcinoma of the head and neck cancer patients (2 of whom received 2 doses each). Any observed side effects were mild. The only side effect that occurred in more than one volunteer/patient was positive WBC esterase in the urinalysis without accompanying urinary symptoms.

Risks associated with Investigational PET/CT Imaging

The administration of the radioactive substance will feel like a slight pinprick if given by intravenous injection. Patients who are claustrophobic may feel some anxiety while positioned in the scanner. Also, some patients find it uncomfortable to hold one position for more than a few minutes. The subjects will not feel anything related to the radioactivity of the substance in their body. The substance amount is so small that it does not affect the normal processes of the body. Procedures such as isotope injection are standard procedures currently used in the clinical PET and Nuclear Medicine clinics and the usual sterile methods will be used.

Risks from PET imaging include exposure to ionizing radiation and the placement of an intravenous line. Total time required for each PET study will be approximately 90-120 minutes. The radiation the participants will receive as a result from participating in this study includes radiation from administration of [¹⁸F]F-AraG and the accompanying CT scans for attenuation correction. This radiation exposure is for research purposes only.

- The amount of radiation dose the healthy group will receive from one of [¹⁸F]F-AraG PET/CT is 11.7-12.3 mSv (2.7mSv from 163MBq for females and 3.3 mSv from 211MBq of [¹⁸F]F-AraG for males plus a further 9mSv from the three CTs (one cardiac and two whole body CT scans) for attenuation correction acquired usually before the PET acquisitions.

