- The amount of radiation dose the GVHD group will receive from one [¹⁸F]F-AraG PET/CT session is 5.7-6.3 mSv (2.7mSv from 163MBq for females and 3.3 mSv from 211MBq of [¹⁸F]F-AraG for males plus a further 3mSv from the whole body CT scans for attenuation correction. If a patient is able to withstand longer times in the scanner they will undergo a further PET acquisition at 30 minutes for which 1 more CT scans will be performed usually before the PET acquisition (and an additional 3mSv dose will be received).

This amount of radiation involves minimal risk and is necessary to obtain the research information desired. Procedures will be in place for verification of correct radiopharmaceutical dose and route of administration (i.e., each dose will be double checked for dosimetry and quality by a researcher and technologist).

Risks associated with aGVHD

Patients highly suspected to have aGVHD or who are at high risk of developing aGVHD may experience side effects from underlying disease while participating in this study. Acute GVHD is characterized by a wide spectrum of host tissue injuries in the gastrointestinal (GI) tract, liver, skin, and lungs; causing a wide range of symptoms [3, 5]. In this setting, a very large number of

Grade 1 and 2 adverse events (AEs) are expected to occur, regardless of whether or not a patient is participating in a research study. Expected AEs include a number of specific AEs that are associated with acute GVHD.

The Protocol Director (PD) or designee will assess each AE to determine whether it is unexpected according to the Informed Consent, Protocol Document, or Investigator's Brochure, and related to the investigation. Unless specifically determined otherwise by the investigator, the following events are considered expected in the early post-transplant setting.

- Alopecia
- Anemia
- Anorexia
- Bleeding, including requiring transfusions
- Cardiac arrhythmias
- Central venous catheter infections
- Constipation
- Diarrhea
- Edema
- Fatigue
- Febrile episodes
- Gastritis
- Graft failure
- Graft versus host disease
- Hematuria
- Hypertension
- Hypotension
- Hypoxia
- Incontinence
- Infections, including sepsis
- Insomnia
- Laboratory abnormalities
- Mental status changes and mood alterations
- Mucositis
- Nausea
- Neutropenia
- Pain
- Pleural effusion
- Pneumonitis
- Rash
- Seizures
- Sinusoidal obstructive syndrome
- Tachycardia
- Thrombocytopenia
- Thrombotic microangiopathy
- Tremor
- Vomiting

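### By default, a serious tracer-related event made up of terms on the 7.1 transplant list does not have to be reported to the IND Holder, because 7.3 counts anything described in the protocol as expected

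*Combined protocol and SAP*

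**What the plan says.** Section 7.3 sets three joint conditions for the 24-hour report to the IND Holder and defines the second of them. The rule begins "Adverse events deemed serious, unexpected (i.e. not described in the protocol"; the same definition also counts the Brochure and the consent forms, and the third condition is that the event is judged tracer-related. The IND Holder then decides whether the event meets the IND safety reporting criteria.

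Section 7.1, under Risks associated with aGVHD, gives a list introduced by "Unless specifically determined otherwise by the investigator, the following events are considered expected in the early post-transplant setting". The subsection is about patients who "may experience side effects from underlying disease while participating in this study". It also says that the Protocol Director, or someone delegated by that role, "will assess each AE to determine whether it is unexpected according to the Informed Consent, Protocol Document, or Investigator's Brochure, and related to the investigation".

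On the tracer itself, 7.1 (Risks associated with this Investigational Agent) says "Any observed side effects were mild". The one finding seen in more than one person was positive WBC esterase in the urine, without symptoms.

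Section 7.3 has two other routes. One is "SAEs Grade 3 and above, and all subsequent follow-up reports will be reported to the Stanford Cancer Institute Data and Safety Monitoring Committee", and this is done "using the study specific CRF regardless of the event’s relatedness to the investigation". After DSMC review, Unanticipated Problems go on to the IRB. The other is the annual report to FDA, which is described for non-serious events.

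**The concern.** How common an event is after transplant helps to answer whether the tracer caused it. It does not answer whether the event is already known for the tracer. Because 7.3 takes the whole protocol as its reference, the transplant list answers both questions. An event that has already been judged related can then be dropped because it is common for another reason.

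The study is the tracer's first use in GVHD patients (10.7), and toxicity is a secondary objective (1.2). The IND Holder is also evaluating the tracer in parallel studies (2.3). It can assess only what it is sent, so a filter at the site can withhold new safety information from the party responsible for acting on it.

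**Working it through.** The plan gives no sample size, power or error rate that bears on this point. The check is a count and a trace of the reporting rule.

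**Count.** The 7.1 list has 37 entries, all distinct. One of them, laboratory abnormalities, is a whole class.

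**Prior human experience (7.1).** Subjects: 6 healthy + 3 bladder cancer + 2 breast cancer + 3 head and neck cancer = 14. Injections: 14 + 2 + 2 repeat doses = 18. With so short a record and only mild effects seen, a serious related event would be new information.

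**Rule.** Report to the IND Holder = serious AND related AND unexpected, where unexpected means absent from the protocol, the Brochure and the consent documents. Presence in the protocol alone is enough to fail the third condition, whatever the other two documents say.

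**Trace, for an event already judged serious and tracer-related:**

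| Event | 24-hour report to IND Holder | Other written routes |
|---|---|---|
| Term in none of the three documents | Required | DSMC if Grade 3 or above |
| Listed term, Grade 3 or above, no override | Not required | DSMC; then IRB if an Unanticipated Problem |
| Listed term, Grade 1 or 2, no override | Not required | AE log (7.2); general DSMC review of serious events (8.3); no recipient named in 7.3 |
| Listed term, investigator overrides | Required if the 7.1 override governs; not on the literal 7.3 definition | As above, by grade |
| Listed term in a healthy volunteer | Not required on the literal 7.3 definition; required if the list is confined to transplant patients and neither the Brochure nor the consent documents describe the event | As above, by grade |

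The Grade 1 or 2 row is possible because 7.2 defines seriousness by outcome, such as hospitalization, and not by grade.

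**Illustration.** An Arm 2 patient has rash, hypotension, hypoxia and tachycardia shortly after injection, recorded under those terms and judged serious and related. All four terms are on the list, so the default is expected and the 24-hour report is not triggered.

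**Is there another path to the IND Holder?** The annual report covers non-serious events. The DSMC's onward route in 7.3 is to the IRB. Section 8.3 sends audit results to the IRB and regulatory authorities. Section 1.1 says critical data will go to FDA but does not define them. None of these names the IND Holder.

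**The case against.** A reader might infer that such an event can never reach the IND Holder. The documents do not support that. Section 7.1 makes the list a default that the investigator can set aside, and it requires expectedness and relatedness to be assessed event by event. An event found unexpected in that way must be reported within 24 hours if the 7.1 override governs. This stands, and it limits the finding to the default. It does not remove the finding: the override has no criteria, and 7.3, which sets the duty to report, defines unexpected in terms that leave no room for it.

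A reader might also infer that the DSMC is the only body to see a Grade 3 or higher event, or that nobody outside the site sees a lower-grade one. Neither holds. Unanticipated Problems go to the IRB within 10 working days of DSMC review, or 5 for deaths and life-threatening experiences. Section 8.3 has the DSMC regularly review serious events with no grade floor. Section 7.3 also has a termination rule for an unanticipated effect that poses unreasonable risk. These are real safeguards, but none leads to the IND Holder.

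Four further points narrow the concern:

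- Laboratory abnormalities are not foreign to the tracer, since the urine esterase finding is one. It was mild, so it says nothing about a serious abnormality.
- The cytotoxicity of AraG should not be used to raise the stakes. Section 2.2 attributes it to drug doses and expects no pharmacological effect at trace mass.
- An investigator could report the illustration above as a single syndrome, such as anaphylaxis, which is not on the list. The outcome then depends on how the event is coded, which is itself a weakness in the rule.
- The list concerns transplant patients, so applying it to a healthy volunteer strains its purpose. The literal 7.3 definition still does so.

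**Conclusion.** The concern holds as a defect in the default. A serious event judged related to the tracer and made up of terms among the 37 does not have to be reported to the IND Holder unless the investigator overrides the list, and 7.1 and 7.3 do not agree on whether that override counts. It affects up to 25 GVHD patients and, on the literal wording of 7.3, the 5 healthy volunteers. How many events would be withheld cannot be estimated from the documents.

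The conclusion rests on reading the 7.3 definition as written. The Investigator's Brochure and consent documents were not available. Their content could add to what counts as expected, but it could not undo the effect of the protocol's own list. The gap concerns the IND Holder only; it does not show that serious events escape independent review.

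**What to change.** In 7.3, state that expectedness for the IND Holder report is judged only against tracer-specific safety information: the Investigator's Brochure and the 7.1 subsection on risks of the investigational agent, at the severity observed. In 7.1, state that the transplant list describes background events and may inform the causality judgement, but does not set expectedness for tracer-related events or for healthy volunteers. These sentences also remove the conflict over the override.

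A simpler alternative is to send every serious event judged related to the IND Holder whatever its expectedness. Either change is enough; both are not needed.

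The cost is two or three sentences and a few more MedWatch forms. Relatedness remains a condition, so background transplant events would not flood the IND Holder.

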8 REGULATORY CONSIDERATIONS

8.1 Institutional Review of Protocol

The protocol, the proposed informed consent and all forms of participant information related to the study (e.g. advertisements used to recruit participants) will be reviewed and approved by the Stanford IRB and Scientific Review Committee (SRC). Any changes made to the protocol will be submitted as a modification to FDA and will be approved by the IRB and SRC prior to implementation. The Protocol Director will disseminate the protocol amendment information to all participating investigators.

8.2 Data Management Plan

The study will be registered on Oncore, a centralized database used by CCTO to manage clinical trials. All associated approvals and subject information will also be stored on this platform. Any case report forms (CRFs) will be stored in a locked office in the Nuclear Medicine clinic. Records will be kept using OnCore.

Data will be managed using Excel software where the following important parameters will be documented; subject ID (number assigned based on order of scan), the type of subject (healthy/highly suspected GVHD or high risk GVHD group), sex of the subject and their weight, height and age. The date and time of radiotracer injection, the dose injected, time and duration of PET scan will also be noted.

For data analysis the following parameters will be documented; region of interest (e.g. liver, heart, cervical lymph nodes), volume of the region of interest and the associated mean, maximum and minimum values for the Standard Uptake Values (SUV).

8.3 Data and Safety Monitoring Plan

During the clinical investigation, the Protocol Director will evaluate the progress of the trial, including periodic assessments of data quality and timeliness, participant recruitment, accrual and retention, participant risk versus benefit, performance of trial sites, and other factors that can affect study outcome. Monitoring of the trial will occur every 8 weeks and a record of monitoring activities will be maintained by the study team.

The Stanford Cancer Institute Data and Safety Monitoring Committee (DSMC) will audit study related activities at least annually in accordance with the DSMC SOP to determine whether the study has been conducted in accordance with the protocol, local standard operating procedures, FDA regulations, and Good Clinical Practice (GCP). This may include review of regulatory binders, case report forms, eligibility checklists, and source documents. In addition, the DSMC will regularly review serious adverse events and protocol deviations associated with the research to ensure the protection of human subjects. Results of DSMC audits will be communicated to the IRB and the appropriate regulatory authorities at the time of continuing review, or in an expedited fashion, as needed.

9 MEASUREMENTS

9.1 Primary and Secondary Outcome measures

Primary outcomes will be the severity/score of aGVHD or the development of aGVHD in the highly suspected and high risk groups respectively. Diagnosis and staging of the disease are ultimately based on skin, liver and gut involvement and will be further supported by the secondary outcome of IHC analysis of the gastrointestinal tract. The latter mostly focuses on the detection of dead regions as determined by haematoxylin and eosin staining. For this study, an additional secondary outcome will be to further stain tissues for T cell markers to determine T cell infiltration (CD3, CD4 and CD8) and T cell activation markers (e.g. OX40) to determine T cell status since activated T cells underlie the development of aGVHD in the early stages.

9.1.1 Primary Outcome Measurement Methods

Static images acquired will be used to determine the bio-distribution of the imaging agent in the GVHD groups. Past images as well as newly acquired data from healthy subjects will be used as comparisons. Regions of interest will be drawn on various organs such as the liver, cervical lymph nodes and gut and quantified using imaging software (e.g. Inveon Research Workplace or Amide). In addition any areas that show up differently in the GVHD groups, to the normal bio-distribution seen in healthy subjects will be identified and ROIs will also be drawn over these regions.

Bio-distribution data will be expressed as % injected dose/gram (%ID/g) and/or as standard uptake values (SUV) with respect to the organ being studied. In the high suspected aGVHD group, [¹⁸F]F-AraG PET results will be compared to any grades and scores of aGVHD severity attributed to subjects. In the case of the high-risk group, after the second scan, patients will be monitored for development of aGVHD and the clinical endpoint (whether or not the high risk patient develop aGVHD) will represent the primary outcome variable. In addition, IHC analysis of biopsies taken in either GVHD group will help in the interpretation of the primary results and thus potentially support interpretation of the PET data. The IHC analysis will involve determining the amount of cell death or T cell infiltration and activation.

Vital signs and blood laboratory data collected before and after the i.v. injection of [¹⁸F]F-AraG will allow evaluation of any unexpected side effects.

To measure plasma radioactivity, whole blood sample will be centrifuged. The radiolabeled tracer concentration in whole blood, pellet post centrifugation and plasma will be measured by a gamma well counter (1-min per sample). The counting rates measured by the well counter will be converted to the PET equivalent counts using a conversion factor from a weekly phantom cylinder study. The counts should be decay corrected back to the injection time.

Plasma parent tracer and metabolite concentrations will be determined using solid phase extraction combined with HPLC technology.

Clinical assessment of disease severity will be made by the aGVHD grade. Staging and grading of the disease will be performed by Clinicians at the Bone Marrow and Transplant Clinic using the Glucksberg grade and International bone marrow Transplant Registry Severity Index (IBMTR) at time of enrollment and imaging.

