5 STUDY PROCEDURES

5.1 Imaging Protocol for Patient Groups

Each subject may have up to two imaging sessions. The procedures for each imaging session is detailed below:

Day 1 (Imaging Day)

Overview of procedures prior and post injection of [¹⁸F] F-AraG:

1. Subject will participate in an informed consent session (approximately 30 minutes) and if she/he would like to continue after being fully informed she/he will sign consent form.
2. Subject will be asked to drink several glasses of water before arriving at the nuclear medicine clinic and during the study.
3. Subject will be interviewed to obtain medical history.
4. Volunteer height and weight will be measured.
5. Baseline Heart Rate (HR), Blood Pressure (BP), Blood Oxygen %, Temperature, and Respiratory Rate will be collected at baseline (5-120 minutes prior to the injection of the tracer).
6. IV line may be placed in both arms of healthy subjects for PET tracer injection and another may be used for blood collection. The GVHD patients will have double lumen catheters which can these be used for these purposes.
7. For baseline CBC analysis- 3 ml of blood will be collected and 5 ml of blood will be collected for baseline metabolic panel analysis.
8. Subject may either be positioned on the PET/CT scanner bed or another bed in the clinic (where possible the same PET-CT system should be used especially for the healthy subjects).
9. Injection of [¹⁸F] F-AraG and post-injection procedures will follow.
10. If possible, subjects should be asked to urinate prior to the start of the PET/CT scans.
11. A bolus < 5.7 mCi of clinical grade [¹⁸F] F-AraG for male volunteers or < 4.4 mCi of clinical grade [¹⁸F]F-AraG for female volunteers will be injected through IV.
12. A CT image will be acquired with the PET images.
13. The PET scanning procedure may start at the time of tracer injection or at a later time point after tracer injection. The imaging field includes the vertex to thigh for healthy subjects and vertex to feet for GVHD patients. Up to two whole-body PET scans may be performed at various time points after injection of the tracer, not to exceed 2 hours after tracer injection.
14. Blood pressure, Temperature, Blood Oxygen saturation, Heart Rate, Respiratory Rate will be measured immediately after [¹⁸F]F-AraG PET-CT procedure.
15. A safety follow up will happen at one time point within the time interval (day 2 – day 7) post-scan.
16. All observed adverse events and subject complaints will be recorded.

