9. Participant will have EKG leads placed for cardiac gating and then be placed in the scanner.
10. A low dose attenuation correction CT scan (ACCT) of the heart will be performed for attenuation correction.
11. A small low activity calibration source of known activity, volume, and concentration of F-18 activity will be taped to the furthest corner of the scanner field of view prior to radiopharmaceutical injection. The 30 minute dynamic PET acquisition of the heart will then begin, making sure that the entire heart region is covered in the field of view. All PET/CT scans should be done on the Discovery MI PET/CT scanner or the PET/CT 690 scanner.
12. Right after the start of the PET acquisition, [¹⁸F]F-AraG formulated in a sterile and pyrogen-free isotonic solution in less than 10 ml will be administered in a single slow IV injection. The line will be slowly flushed at a constant rate with at least 10 ml normal saline after injection.
13. The initial 5 minutes of the dynamic PET scan will be finely acquired at 5 seconds/frame (total number of frames in initial 5 minutes =60 frames) so as to capture the peak of the cardiac input function and then 1 minute/frame for the next 25 min over the same field of view (FOV). The dynamic PET data should be collected in list-mode and saved

appropriately.

14. Participants will have skull base-to-thigh static PET-CT scans (which includes the brain) obtained again at 60 and 90 minutes (scans #2 and #3). CT will use 120 kV and dose modulation based on body habitus, ranging 10-105 mA for both scans.
15. Blood pressure, temperature, respiratory rate, heart rate and pulse oximetry measurements will be performed post scan 3.
16. All recordings of important time measurements (e.g. time of injection and acquisitions) will be done using the same clock e.g. a phone.
17. Participants will be asked to void frequently to reduce radiation exposure.
18. Adverse drug events that have developed during the scans will be recorded in source documents. Any that develop after $[^{18}\text{F}]\text{F-AraG}$ injection will also be recorded in the source documents when patients seen at the safety follow-up visit at one time point within the time interval (day 2 – day 7) post-scan.

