9.1.3 Response Review

The SUVmax values will be analyzed by Nuclear Medicine and Radiology physicians blinded to the diagnosis and results of the other scan, in a randomized order to avoid bias. IHC values will be assessed by trained Pathologists.

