10.5 Analysis

10.5.1 Analysis Population

Analysis population: all ROIs drawn on various organs, as well as areas with elevated SUV relative to healthy volunteers.

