10.8 Accrual estimates

We expect the accrual of 5 healthy volunteers and 25 patients over 24-36 months.

Approximately 1-2 high risk patients for GVHD are seen monthly in the Bone Marrow and

Transplant clinic at Stanford Cancer Institute. Established GVHD patients are frequently seen in the clinic (approximately 5 high intensity and 10 low intensity patients at a given time). We consider this planned accrual achievable given our experience with other protocols and the expressed support from the referring physicians, [name] and [name].

We plan to prioritize patients from Arm 1; imaging up to 10 patients highly suspected to have aGVHD and analyze scans to ascertain if the tracer is able to image the disease, before recruiting patients from Arm 2 (those that are at high risk of developing the disease post transplant).

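### Only GVHD scans are searched for abnormal uptake, with no cut-off and no masking to group, so no false-positive rate is planned for a flagged area

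*Combined protocol and SAP*

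**What the plan says.** Section 9.1.1 has ROIs drawn on named organs. It adds that "any areas that show up differently in the GVHD groups, to the normal bio-distribution seen in healthy subjects will be identified", with further ROIs drawn there. The healthy images are the yardstick: "Past images as well as newly acquired data from healthy subjects will be used as comparisons". Section 10.5.1 defines the primary analysis population as "all ROIs drawn on various organs, as well as areas with elevated SUV relative to healthy volunteers". Neither section gives a numeric rule for elevated, and neither says who carries out the search.

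Section 9.1.3 covers the analysis of SUVmax values. The physicians doing it are "blinded to the diagnosis and results of the other scan, in a randomized order to avoid bias".

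On the imaging field, Section 5.1 states: "The imaging field includes the vertex to thigh for healthy subjects and vertex to feet for GVHD patients". The healthy-subject steps in the same section say "Participants will have skull base-to-thigh static PET-CT scans (which includes the brain) obtained again at 60 and 90 minutes", and Table 6-1 also ends these scans at the thigh. The GVHD steps and Tables 6-2 and 6-3 run from head to toe at 60 minutes, with an optional scan at 30 minutes, in both arms.

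Section 10.8 plans to image up to 10 Arm 1 patients first and "analyze scans to ascertain if the tracer is able to image the disease, before recruiting patients from Arm 2". Section 1.1 promises performance on a per-lesion basis.

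**The concern.** The rule that creates extra ROIs works on one side only. A GVHD scan is searched for whatever stands out from healthy uptake, and a healthy scan never is. The comparator thus does not undergo the test that it is meant to calibrate, and the plan has no count of how often the search flags a person without GVHD.

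The search also needs to know the group, and an uncropped image shows it. Below the thigh the rule applies to patients although the new volunteers contribute nothing there.

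Two uses of the scans are exposed. One is the per-lesion performance aim. The other is the judgement in Section 10.8 that the tracer images the disease, which opens Arm 2 and has no stated criterion. A smaller effect reaches Section 10.5.2. There the Arm 1 analysis correlates the median or maximum SUV across ROIs with severity, and adding areas because they look high can raise a patient's maximum. Nothing says that the person who searches is blind to grade.

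**Working it through.** **The plan's own figure.** There is none to reproduce. Section 10.7 gives up to 25 GVHD patients and 5 healthy volunteers without alpha, power or effect size. Under the plan as written, no healthy scan is searched, so a false-positive rate in healthy subjects has a denominator of 0.

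**Inputs from the documents**
- New healthy volunteers: 5 (Section 10.7).
- Past healthy volunteers: 6, from another site, with SUVs at 47-77 minutes (Section 2.2). Together 5 + 6 = 11.
- Arm 2: roughly half of 25, so 12 or 13 patients (Section 10.7).
- GVHD incidence: 20-50% with related donors, upwards of 70% with HLA-matched unrelated donors (Section 2.1).

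**Assumptions, not in the documents:** normal SUVs, independent regions, 5 or 10 regions per scan, and a cut-off of healthy mean + 2 SD.

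**Step 1. One normal region.** A new normal value exceeds the mean + 2 SD of n healthy values with probability p = P(t with n-1 df > 2/√(1+1/n)).
- n = 11: 2/√(12/11) = 1.915 on 10 df, p = 0.042.
- n = 5: 2/√1.2 = 1.826 on 4 df, p = 0.071.

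**Step 2. At least one flagged area in k regions:** 1-(1-p)^k.

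| Healthy scans | p per region | k = 5 | k = 10 |
|---|---|---|---|
| 11 (past and new) | 4.2% | 19% | 35% |
| 5 (new only) | 7.1% | 31% | 52% |

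The second row applies only if the past scans cannot be matched. Positive correlation between regions lowers all the k = 5 and k = 10 figures.

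**Step 3. Why the cut-off matters.** If elevated meant above the highest of 11 healthy values, p = 1/12 = 8.3%, giving 35% (k = 5) and 58% (k = 10). When each healthy scan is compared with the other 10, this rule flags exactly one healthy subject per region, ties aside. That is 1/11 = 9.1% whatever the data, so the rule cannot measure its own false-positive rate.

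**Step 4. What a matching search could show.** With 0 of m flagged, the exact two-sided 95% upper limit is 1-0.025^(1/m).
- Healthy: m = 11 gives 28.5%; m = 5 gives 52.2%. One flagged of 11 gives 0.2% to 41.3%.
- Arm 2 without aGVHD: at 20% incidence, 12 × 0.8 = 9.6 or 13 × 0.8 = 10.4, about 10. At 50%, 6 or 6.5, about 6. At 70%, 3.6 or 3.9, about 4. The upper limits with none flagged are 30.8%, 45.9% and 60.2%.

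**Step 5. What the field of view reveals.** Healthy scans end at the thigh; both GVHD arms run to the feet. The field therefore separates healthy from GVHD. It does not separate Arm 1 from Arm 2, one grade from another, or patients who later develop aGVHD from those who do not.

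**The case against.** A reader might infer that the blind in Section 9.1.3 collapses. The documents do not support that. The section masks diagnosis and the other scan's result, and it does not claim to mask healthy versus patient. The planned tests in Sections 10.5.2 and 10.6.2 all lie within the GVHD groups. What they need hidden is grade, later aGVHD, the other scan and the IHC result, and neither the field of view nor Arm 1 membership reveals any of these. Section 9.1.1 is also written in the passive, so it is only an inference that the SUVmax readers perform the search.

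A reader might also infer that no one without GVHD is ever searched. That is wrong as well. Arm 2 patients get the same search and field, and some will stay free of aGVHD; negative biopsies may add site-level information. What is missing is a cut-off and a planned tabulation.

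Three further objections are fair. The percentages rest on assumed cut-offs and region counts. SUV enters the tests as a continuous value. This is also a pilot that disclaims formal power. They reduce the size of the point. They do not supply the missing rule, the matching search or the false-positive count, on which the per-lesion aim and the Arm 2 decision depend.

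The leg gap is stated for the new volunteers only. Section 2.2 calls the six past scans whole-body without giving their lower limit.

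**Conclusion.** The point holds in a limited form. The search for abnormal areas is one-sided, has no stated cut-off, is not masked to healthy versus GVHD, and is applied below the thigh without a reference from the new volunteers. No false-positive rate is planned, although Arm 2 patients without aGVHD could supply one. Failure of the Section 9.1.3 blind to grade, outcome or the other scan is not shown.

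The size is illustrative: 19% to 35% of normal people with at least one flagged area, given 11 healthy scans, a mean + 2 SD rule and 5 to 10 independent regions. The figures show that false areas could be common and would go uncounted; they do not predict this trial's rate. The main effect is on the per-lesion aim and the opening of Arm 2, more than on the within-group correlations. The change is worth making because it alters what the pilot can conclude and needs no new scans.

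**What to change.** Amend Sections 9.1.1, 9.1.3 and 10.5.1 as follows.

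- **(a) Rule and field.** Fix one numeric rule for elevated in advance, for example the region-specific healthy mean + 2 SD rather than the healthy maximum. Apply it only within the field shared with healthy scans, at about 60 minutes, using past scans where their field and timing match. List uptake below the thigh descriptively, in a separate read.
- **(b) Equal search.** Have the existing readers apply the same search to coded, cropped healthy and GVHD scans in random order, masked to group, grade and outcome as far as the images allow. Compare each healthy scan with the remaining healthy scans. Cropping may not hide everything: EKG leads, catheters and CT settings differ between the groups (Section 5.1).
- **(c) Reporting.** Give the share of subjects with a flagged area, with exact 95% limits, in healthy subjects, Arm 2 without aGVHD, Arm 2 with aGVHD, and Arm 1. Show the two Arm 2 scans separately, so that a second scan does not count as a second chance.
- **(d) Final values.** Take the final SUVs from this end-of-study read. Use the Section 10.8 look only to decide on opening Arm 2.

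The cost is wording and reading time. Early Arm 1 scans are read twice, the legs need a separate read, and leg uptake leaves the comparative analysis. The healthy rate stays imprecise, as the limits in Step 4 show, but it replaces a rate that the plan would not measure at all.
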